Document Number:	c39406431-01		
EudraCT No. EU Study No.	N/A			
BI Study No.	1490-0005			
BI Investigational Product(s)				
Title	A multi-center, longitudinal 12-week pilot study to evaluate cough severity and its impact, utilizing a next generation cough monitor, in participants with idiopathic pulmonary fibrosis (IPF) or Non IPF Pulmonary Fibrosis			
Lay Title	A study in people with pulmonary fibrosis to monitor cough with a wearable device			
Clinical Phase	N/A			
Clinical Trial Leader	On behalf of			
	Phone / Fax: Email:			
Coordinating Investigator	Phone			
	Email:			
Current Version and Date	Version 1.0 / 16 Sep 2022			
Original Protocol Date	16 Sep 2022 Page 1 of 71			
© 2022 Bochringer Ingelheim This document may not - in full of	Proprietary confidential information. © 2022 Boehringer Ingelheim International GmbH or one or more of its affiliated companies. All rights reserved. This document may not - in full or in part - be passed on, reproduced, published or otherwise used without prior written permission.			

16 Sep 2022

Protocol

Page 2 of 71

Proprietary confidential information © 2022 Boehringer Ingelheim International GmbH or one or more of its affiliated companies

PROTOCOL SYNOPSIS

Company name	Boehringer Ingelheim
Original Protocol date	16 Sep 2022
Revision date	N/A
BI study number	1490-0005
Title of study	A multi-center, longitudinal 12-week pilot study to evaluate cough severity and its impact, utilizing next generation cough monitoring, in participants with idiopathic pulmonary fibrosis (IPF) or Non IPF pulmonary fibrosis.
Coordinating Investigator	
Study site(s)	Multi-centre study in approximately 5-7 countries.
Clinical phase	N/A
Study rationale	A further understanding of the similarities and differences in cough among persons with Non IPF forms of pulmonary fibrosis and IPF, together with insight into the pattern and impact of cough in these patients is required. The current pilot aims to assess cough frequency, indirect measures of cough intensity and the association between objective cough measures and lung physiology and various patient-reported outcome measures in a patient cohort with Non IPF forms of pulmonary fibrosis and IPF.
Study objective(s)	The primary objective of this study is to objectively quantify cough frequency over 12 weeks in a cohort of subjects with IPF or Non IPF pulmonary fibrosis using a digitally enabled cough monitor. Additionally, we will assess the feasibility of hybrid study design, utilizing cough monitoring and remote video-assisted home spirometry.
Study endpoints	 Primary Endpoint: Cough count per hour (CC/hr) measured over a 24-hour period at baseline visit, Week 4(V4), Week 8(V5), Week 12 (V6). Secondary Endpoints: Change from baseline in CC/hr at Week 4, Week 8, Week 12 FVC (mL) at baseline FVC (mL) at Week 12 Change from baseline in FVC (mL) at Week 12 Feasibility of remote cough data capture (defined as % of analysable data per 24-hour recording) Feasibility of hybrid study design (successful completion of all elements of remote visit)
Study design	Low intervention, 12-week pilot study, utilizing a digitally enabled cough monitor and hybrid study design, in subjects with IPF or Non IPF pulmonary fibrosis.

Page 3 of 71

Proprietary confidential information © 2022 Boehringer Ingelheim International GmbH or one or more of its affiliated companies

Total number of	50		
patients	50		
Number of nationts non	50		
Number of patients per	50		
Diagnosis	Idionathic Pulmonary Fibrosis (IPF) or Non IPF nulmonary fibrosis		
Main inclusion and	Inclusion:		
exclusion criteria			
	• Subject \geq 18 years old		
	• Subject diagnosed with IPF by ATS/ERS/JRS/ALAT guidelines		
	or Non-IPF Pulmonary Fibrosis ($\geq 10\%$ fibrosis on HRCT as per		
	PI assessment) within the past 12 months		
	 FVC > 40% predicted at baseline 		
	 Life expectancy > 6 months (per assessment of treating 		
	physician)		
	Exclusion:		
	Current smokers		
	• Upper respiratory tract infection (URTI) or Lower respiratory		
	tract infection (LRTI) [including COVID-19 infection] within 4		
	weeks		
	• Airflow obstruction (FEV1/FVC < 0.70) at baseline or known		
	history of significant spirometry response to BD		
	• Initiation or change in dose or type of anti-fussive medication.		
	angiotensin-converting enzyme (ACE) inhibitors or		
	corticosteroids in the 4 weeks prior to study entry		
	 Initiation or change of onjate dose within 4 weeks of study entry. 		
	 Subject with II D exception as defined by the investigator 		
	• Subject with ILD exacerbation as defined by the investigator within 4 weeks prior to study entry		
Dovice	while 4 weeks prior to study entry		
Device	Weenshie Couch Menitor		
Made of administration			
Mode of administration	I ranscutaneous - adheres to chest wall		
Comparator product(s)	Not applicable		
Duration of assessment	12 weeks		
Statistical methods	Descriptive statistics will be presented for all primary and secondary		
	endpoints. Additionally, CC/hour will be log transformed and		
	summarized in terms of geometric mean and 95% confidence		
	intervals.		

Page 4 of 71

Proprietary confidential information © 2022 Boehringer Ingelheim International GmbH or one or more of its affiliated companies

FLOW CHART

Study Periods	Screening*	Baseline* Visit	Remote Study Visits				EoS Visit
Visit	1	2	3	4	5	6	7/EoS
Days	- 1 wk	1	3	28	56	82	84
Time window for visits			+ 2 days	$\pm 5 \text{ days}$	$\pm 5 \text{ days}$	- 2 days	$\pm 5 \text{ days}$
Informed consent	Х						
Review of in-/exclusion criteria	Х						
Demographics	Х						
Smoking Status/history	Х						
Medical history (Comorbidities)	Х						
Pregnancy status (where available)	Х						Х
COVID-19 history (including vaccination status)	Х						
Non IPF Pulmonary Fibrosis (including ILD diagnosis category) or IPF	Х						
Progressive Pulmonary Fibrosis Phenotype (Y/N)	Х						
Concomitant therapy (including prescription medications for Pulmonary Fibrosis)		Х		Х	Х		Х
Historical Pulmonary Function Tests (FVC & DLCO) ²	Х						
Historical HRCT Pattern ³ (UIP, Probable UIP, Indeterminate for UIP, Inconsistent w/UIP)	Х						
Physical examination		Х					Х
Vital signs ⁴		Х					Х
SpO ₂		Х					Х
In-Office Spirometry ⁵		Х					Х
Distribute & provide instruction on cough monitor		Х					
Distribute & provide instruction on home spirometer		Х					
Home Spirometry			X ^{7,9}	Х	Х	X ^{7,9}	
Reporting of AEs/SAEs ¹⁰ & Unscheduled clinical visits		Х		Х	Х		Х
Videoconference remote visit				Х	Х		
24-hour cough monitor recording ¹¹		Х		X ¹¹	X ¹¹	X ¹¹	
24-hour cough monitor data upload ¹²		Х		Х	Х	Х	
Remote Procedures Compliance Check 13							
(Home spirometry, Videoconference remote visit (V4, V5), Cough recordings)			Х	Х	Х	Х	
Return of cough monitor & home spirometer							Х
Patient survey regarding use of cough monitor and home spirometer							Х

Boehringer Ingelheim BI Study No.: 1490-0005 c39406431-01

Protocol

Proprietary confidential information © 2022 Boehringer Ingelheim International GmbH or one or more of its affiliated companies

Study Periods	Screening*	Baseline* Visit	Remote Study Visits			EoS Visit	
Visit	1	2	3	4	5	6	7/EoS
Days	- 1 wk	1	3	28	56	82	84
Completion of patient participation							х

*Screening and Baseline Visit can occur on the same day.

- Most proximate historical FVC & DLCO within 6 months and most distant FVC & DLCO within 12 months should be recorded
- 3) Most proximate historical HRCT performed within the previous 12 months
- 4) Measurements of vital signs should precede blood sampling
- 5) Site personnel should confirm that FVC continues to meet eligibility criteria for study inclusion prior to preceding with additional study procedures
- Patients will need to complete home spirometry within 72 hours, but not on the same day as Visit 2/Baseline study visit.
- 8) Patients will need to complete home spirometry in the 72 hrs preceding the day of Visit 7/EoS
- 9) Efforts should be made to perform spirometric measurements at approximately the same time of the day, at least within the same half-day (morning vs afternoon).
- 10) As described in Section 5.2.6.1.1
- 11) 24-hour cough recording should be initiated immediately following the end of the remote visit.
- 12) 24-hour cough recording data upload should occur immediately after completion of 24-hour CC recording. Patients should place the biosensor on the charger next to the study provisioned mobile phone to allow for data to upload.
- 13) Study personnel conducting the visit will review whether the intended procedures for the visit have been completed. If not, the study team will inquire as to whether the patient requires assistance with any specific aspects of the visit. Site staff will receive notification via email each time a patient completes a cough count recording with successful data upload. If the site does not receive this type of notification, the site should contact the patient to assess whether the patient requires assistance with any elements of the 24 hour cough recording and upload.

 P4U6451-U1
 Protocol
 Page 6 of 71

 Proprietary confidential information © 2022 Boehringer Ingelheim International GmbH or one or more of its affiliated companies

TABLE OF CONTENTS

TITLE PA	AGE	1
PROTOC	OL SYNOPSIS	2
FLOW CI	HART	4
TABLE O	PF CONTENTS	6
ABBREV	IATIONS AND DEFINITIONS	9
1.	INTRODUCTION	.12
1.1	MEDICAL BACKGROUND	.12
1.2	DEVICE PROFILE	.13
1.3	RATIONALE FOR PERFORMING THE STUDY	.14
1.4	BENEFIT - RISK ASSESSMENT	.14
1.4.1	Benefits	.14
1.4.2	Risks	.15
1.4.3	Discussion	.15
2.	STUDY OBJECTIVES AND ENDPOINTS	.16
2.1	MAIN OBJECTIVES, PRIMARY AND SECONDARY ENDPOINTS	.16
2.1.1	Main objectives	.16
2.1.2	Primary endpoint(s)	.16

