1.4.2 Risks

The risks of utilizing a wearable cough monitor are minimal. Skin irritation caused by the adhesive used to apply the device to the chest wall is possible, though not anticipated, and if present would not be expected to be severe. Continuous audio recordings may raise concern for privacy breaches and/or inadvertent recording of conversations. The biosensor data is fully encrypted on device and in transit to prevent unauthorized access to health information. If does not contain an open-air microphone and is not designed to acquire speech or other sounds from a patient's mouth. It is intended to acquire sounds of the lungs and airways including cough sounds, wheeze sounds and normal breath sounds. The file is reversed to avoid discernible speech (if incidentally acquired) being interpretable during a QA/QC session in addition to a speech filter being applied to the raw transmission data to remove speech signatures from review. Files are broken up into short <60 second segments to reduce the risk further of any post-processed file containing discernible speech over a long enough period of time to capture private conversations and information.

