5.2 ASSESSMENT OF SAFETY

5.2.1 Physical examination

A complete physical examination will be performed at Visit 2 and 7, as specified in the Flow Chart. It includes at a minimum general appearance, neck, lungs, cardiovascular system, abdomen, extremities, and skin. Measurement of height and body weight will be performed at Visit 2 and 7. The results must be included in the source documents.

16 Sep 2022

Protocol

Proprietary confidential information © 2022 Boehringer Ingelheim International GmbH or one or more of its affiliated companies

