If a patient misses a visit, the site is asked to alert the contracting entity to determine if the visit should be rescheduled. Subjects are free to discontinue or withdraw from the study at any time. Reason for discontinuation or withdrawal will be collected; however, reasons for withdrawal of consent do not have to be disclosed. Unless otherwise requested by the participant, all data obtained up to consent withdrawal will be retained in the database.

Screening Period (Visit 1)

- Following provision of informed consent, Inclusion & Exclusion criteria should be reviewed as per the FC
- During the screening visit, demographic information will be collected.
 - Age on the day of informed consent (in years)

- Sex (male, female; to describe the patient's sex at birth)
- Ethnicity and race in order to sufficiently characterize the patient population, to support possible subgroup analyses if needed unless not acceptable according to local regulations.
- Medical history (Comorbidities, COVID-19 infection history and vaccination status)
- Pregnancy status (where available)
- Non IPF pulmonary fibrosis (including ILD diagnosis category) or IPF Diagnosis
- Presence or absence of progressive pulmonary fibrosis (PPF) phenotype
- Smoking status/history
- Concomitant medications
- HRCT pattern (most recent study within previous 12 months)
- FVC & DLCO (most recent value within 6 months prior to V2 & most distant value within 12 months of V2)

Visit 2/Baseline Visit – On site

The Screening Visit and Baseline Visit can occur on the same day.

Vital signs will be taken, and a physical exam performed. Subsequently, a pulmonary function test will be performed to measure FVC.

Instructions for utilizing and storing the cough monitor will be reviewed. The patient will place the biosensor onto their chest wall with supervision and assistance (as needed) from the study team. The sensor will be set and started on recording mode for the planned 24hrs. recording. At completion of 24hrs. of recording the next day, the patient will place the charger to allow for data upload via Bluetooth connected app on the study-provided mobile phone. The sensor will be charged for the next visit and stored as per vendor instructions until the next recording at Visit 4. At Visit 2, patients will additionally receive a home spirometer and instructions for use will be reviewed with the patient including access to the video assist portal on the provisioned mobile phone for study use.

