Visit 3- Remote

On Day 3 of the study (+ 2 days) the patient is asked to complete home spirometry (Visit 3) via video-assisted supervision by a trained member of the site study team.

Visit 4 - Remote

Visit 4 (V4) will occur on the 28th day (+/- 5 days) after study enrollment/baseline visit. Visit 4 will be fully remote.

Page 35 of 71

Proprietary confidential information © 2022 Boehringer Ingelheim International GmbH or one or more of its affiliated companies

On the day of the visit, the participant will logon to the platform for a videoconference visit with the site study team preceding home spirometry.

Subsequently, interval history will be obtained, followed by video-assisted supervised home spirometry with the site study team. Immediately following the end of the study visit, the patient will initiate a 24-hour cough recording. At completion of 24 hrs. of recording the next day, the patient will remove the sensor from their chest wall and place the sensor onto a charger to allow for data upload via Bluetooth connected app on the study-provided mobile phone. The charger will be placed next to the study provided mobile phone, which is "pre-loaded" with the sensor for data upload.

The sensor will be charged for the next visit and stored as per vendor instructions until the next recording at Visit 5.

Visit 5 - Remote

Visit 5 (V5) will occur on the 56th day (+/- 5 days) after study enrollment/baseline visit. Visit 5 will be fully remote.

On the day of the visit, the participant will logon to the platform for a videoconference visit with the site study team preceding home spirometry.

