Subsequently, interval history will be obtained, followed by video-assisted supervised home spirometry with the site study team. Immediately following the end of the study visit, the patient will initiate a 24-hour cough count recording. At completion of 24 hrs. of recording the next day, the patient will remove the sensor from their chest wall and place the sensor onto a charger to allow for data upload via Bluetooth connected app on the study-provided mobile phone. The charger will be placed next to the study provided mobile phone, which is "pre-loaded" with the place app, to allow for data upload. The sensor will be charged for the next visit and stored as per vendor instructions until the next recording at Visit 6. The site study team will confirm that the prior 24-hour cough recording was completed and offer to assist the patients with any part of the 24-hour cough recording that they were having trouble with.

Visit 6- Remote

Visit 6 will occur on the 82nd day (-2 days) prior to the EoS visit. On the day of the study visit, the patient is asked to complete home spirometry (Visit 6) via logon to the platform for video supervision by a spirometry trained member of the site study team. Immediately following the end of the study visit, the patient will initiate a 24-hour cough recording. At completion of 24 hrs. of recording the next day, the patient will remove the sensor from their chest wall and place the sensor onto a charger to allow for data upload via Bluetooth connected app on the study-provided mobile phone. The charger will be placed next to the study provided mobile phone, which is "pre-loaded" with the provided app,

Proprietary confidential information © 2022 Boehringer Ingelheim International GmbH or one or more of its affiliated companies

to allow for data upload. Once data upload is complete, the sensor and study provided phone will be stored for return to the site at the EoS visit (Visit 7).

Visit 7 – On site

The End of Study Visit (EoS/V7) will occur on the 84th day (+/- 5 days) following study enrollment/baseline visit.

Interval history will

be obtained; vital signs and a physical exam will be performed. Participants will then undergo spirometry on-site.

The and home spirometry devices will be returned to the site as will the provisioned mobile phone.

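### No adverse-event prompt is scheduled at Visit 3, so skin reactions to the first sensor wear are first due to be asked about 21 to 31 days after removal

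*Protocol*

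**What the plan says.** **Schedule.** The AE/SAE row of the protocol flow chart, which also covers "Unscheduled clinical visits", is marked at Visits 2, 4, 5 and 7/EoS and blank at Visits 1, 3 and 6.

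**First wear.** At Visit 2 (Section 6.1): "The sensor will be set and started on recording mode for the planned 24hrs. recording". The patient takes the sensor off the next day.

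**Contact at Visit 3.** Section 6.1: "On Day 3 of the study (+ 2 days) the patient is asked to complete home spirometry (Visit 3) via video-assisted supervision", with a trained site team member on the call. Visit 6 is similar, with "video supervision by a spirometry trained member of the site study team".

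**Next AE entry.** Section 6.1: "Visit 4 (V4) will occur on the 28th day (+/- 5 days) after study enrollment/baseline visit". Section 6.1 provides for an interval history at Visits 4, 5 and 7 but not at Visits 3 or 6. Flow chart footnote 13 asks staff at the remote visits only whether the planned procedures were done.

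**Named risk.** Section 1.4.2: "Skin irritation caused by the adhesive used to apply the device to the chest wall is possible, though not anticipated". Section 1.4.2 does not expect it to be severe if it occurs.

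**Skin examination.** Section 5.2.1: "A complete physical examination will be performed at Visit 2 and 7". Skin is among the body systems listed.

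**Collection and reporting.** Section 5.2.6.1.1 makes procedure-related AEs recordable, and Section 5.2.6.2.1 runs collection from consent to the EoS visit. Section 8.3.1 makes the AE onset date mandatory. Protocol Section 7.2.6 tabulates frequency and severity of procedure-related AEs. SAP Section 7.8.1 counts subjects with an AE, not events.

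**The concern.** An adhesive reaction would be expected during the 24-hour wear or soon after it. The Visit 2 entry cannot capture a reaction to the first wear, because the sensor goes on at that visit after the physical examination. Visit 3 falls when such a reaction would still be visible or fresh in memory, and staff are already on video with the patient. The SAP's feasibility questions (Section 7.5.2) even ask at Visit 3 whether the cough recording was completed. Yet no AE question is scheduled there.

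At stake is the quality of the safety information on the adhesive. If a mild, brief event is first asked about weeks later, some patients may not mention it. Those who do must recall its onset and severity, and the first is a mandatory field while the second is tabulated. Section 1.3 presents this pilot as a possible model for later interventional trials, so its tolerability data are likely to be reused.

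**Working it through.** The plan states no figure for this interval, so the check is day arithmetic on the visit schedule.

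**Inputs**
- Nominal days from the flow chart: Visit 2 = 1, Visit 3 = 3 (+2), Visit 4 = 28 (±5), Visit 5 = 56 (±5), Visit 6 = 82 (−2), Visit 7 = 84 (±5).
- Each recording starts at its visit and ends the next day (Section 6.1).
- AE row: Visits 2, 4, 5 and 7. The column reading can be cross-checked. The videoconference row falls on Visits 4 and 5, which is what the label of the compliance row says. The concomitant-therapy row has the same pattern as the AE row.

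**First wear, as planned.** Gap = day of next AE entry − day of removal.
- Removal: Day 1 + 1 = Day 2.
- Visit 4 window: 28 − 5 = Day 23 to 28 + 5 = Day 33.
- Nominal gap: 28 − 2 = 26 days (3.7 weeks).
- Range: 23 − 2 = 21 days to 33 − 2 = 31 days (3.0 to 4.4 weeks).
- If the Section 6.1 wording is read as 28 days after a Day 1 baseline, Visit 4 is Day 29 and the range is 22 to 32 days.

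**First wear, with a prompt at Visit 3.** Visit 3 is on Day 3 to 5, so the gap is 3 − 2 = 1 day to 5 − 2 = 3 days.

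**All wears, nominal days**

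| Wear | Off | Next AE entry as planned | Gap | With Visit 3 marked | With Visits 3 and 6 marked |
|---|---|---|---|---|---|
| 1 | Day 2 | Visit 4, Day 28 | 28 − 2 = 26 | 3 − 2 = 1 | 1 |
| 2 | Day 29 | Visit 5, Day 56 | 56 − 29 = 27 | 27 | 27 |
| 3 | Day 57 | Visit 7, Day 84 | 84 − 57 = 27 | 27 | 82 − 57 = 25 |
| 4 | Day 83 | Visit 7, Day 84 | 84 − 83 = 1 | 1 | 1 |

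Marking Visit 3 changes the first wear materially and no other. Marking Visit 6 shortens the third gap by 2 days and cannot capture the fourth wear, which starts after that visit. Wears 2 and 3 keep gaps of about four weeks, because no intervening contact is scheduled before Visit 5 (wear 2) or Visit 6 (wear 3).

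**The case against.** The strongest reply is that AE collection does not depend on the flow chart marks. Section 5.2.6.2.1 requires it continuously from consent, and it also requires detailed AE records in the patient files. A reaction mentioned at Visit 3 must be recorded, and nothing bars staff from asking. This stands. A reader might infer from the blank cell that reactions at Visit 3 go uncollected, or that the protocol contradicts itself. Neither follows: only the scheduled prompt is missing.

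Second, the tabulated rate is fairly robust to missed events. The SAP counts subjects, so a patient who reacts to several wears is counted if any one reaction is captured. The fourth wear is followed nominally 1 day after removal by an AE question and a skin examination. The subject count therefore loses only patients whose reactions were confined to earlier wears and who mention them at no prompt. This also stands, and it is why the rate may be biased low rather than certainly so. It does not help with onset date or severity.

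Third, Visits 3 and 6 are spirometry sessions and do not appear in the videoconference row. That is true of the row, but Section 6.1 puts a trained site team member on live video at both.

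Fourth, the end-of-study survey (Section 10.4) asks about comfort and ease of removal. It is optional and retrospective. Its visible cough-monitor items contain no direct question about a skin reaction, so it supplements AE collection without replacing it.

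Finally, this is a design choice about a risk described as unlikely and not severe. That limits its weight, but the remedy is correspondingly cheap.

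**Conclusion.** The point holds as a low-cost improvement to safety data capture. After the first wear, the first scheduled AE question comes 21 to 31 days after sensor removal (26 nominal), although live contact takes place 1 to 3 days after it. Mild, short-lived skin reactions to that wear may be under-reported or poorly dated and graded in the procedure-related AE table.

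This rests on two assumptions: that such reactions are brief, and that recall of them weakens over three to four weeks. The direction is plausible, but the documents give neither a reaction rate nor a recall rate, so no percentage can be attached to the loss.

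A reader might extend the point equally to Visit 6. The arithmetic does not support that: a mark there moves the third-wear gap only from 27 to 25 days. Nor does a mark at Visit 3 cure recall generally, since wears 2 and 3 keep gaps of 25 to 27 days on nominal days whichever marks are added. No primary or secondary endpoint is affected.

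**What to change.** - **Visit 3:** mark the AE/SAE row. On the existing call, staff ask about any skin problem at the sensor site and record a positive answer under Section 5.2.6.1.1 as procedure-related, noting which wear it followed.
- **Visits 4, 5 and 7:** ask the same wear-specific question within the AE enquiry already scheduled. This matters because the gaps after wears 2 and 3 cannot be shortened much with the existing contacts.
- **Visit 6 (optional):** a mark here has its value in the timing, because the question comes before the fourth sensor is applied.
- **If visits are already complete** (the SAP is dated April 2024): state beside the procedure-related AE table at which visits AEs were scheduled to be asked about and the interval from each wear.

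The cost is one flow chart mark (two with Visit 6) and about a minute per call. The downside is that the reported frequency of mild skin events may rise.
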